## 4.2 *Study Implementation*

This study will be conducted in accordance with the procedures and policies established by CBER-FDA, Office of Biotechnology Assessment (OBA), the Institutional Biosafety Committee (IBC) and the IRB. The study and consent form will be discussed fully with each patient and informed written consent obtained.

### **Treatment must begin within 4-weeks of registration.**

Study Agent Administration (see **Appendix C**)

The dorgenmeltucel-L immunotherapy cells will be injected intradermally (i.d.) using tuberculin or other small syringe with a #25-gauge needle. Injections will be administered as divided doses and administered on an alternating basis with each immunotherapy cycle given in the upper and/or lower extremities. Immunizations will be avoided within an extremity that has previously undergone a complete lymph node dissection.

Patients will be monitored before and after each injection by the nursing staff.

- Monitoring is to include: temperature (T), pulse (P), blood pressure (BP) and respiratory rate (R), measured within 30 minutes before administration of the immunotherapy, and then within 30 minutes after the immunization. In addition, patients will be monitored for signs of acute allergic reactions including local or disseminated skin rash and other adverse reactions.
- Should an adverse event occur after discharge, patients will be instructed to immediately contact the Principal Investigator, Associate Investigator or research nurse for further evaluation and/or treatment.
- Patients developing Grade 2 or greater acute adverse reactions will be monitored for an additional 1-2 hours or until the AE has resolved to less than Grade 2. Medically indicated treatment of the AE will be administered. If an acute AE of Grade 2 or greater persists for more than 4-hours despite observation and/or treatment, a decision on whether to continue observation, institute or modify treatment of the AE, or admit the patient to the inpatient unit for further observation and/or treatment will be made by the Principal Investigators or designees.

A detailed description of the immunotherapy, storage, handling and reconstitution for immunization may be found in Section 6.1.

## 4.3 *Supportive Care*

Patients are to be monitored during each immunization as described above in Section 4.2. Unexpected adverse events will be treated as medically indicated by the involved physicians. Complications of the patient's underlying melanoma or co-morbid medical conditions unrelated to the study treatment will be treated promptly by the study physicians with referral back to the patient's primary medical care provider as appropriate.

#### 4.4 *Duration of Therapy*

Patients whose tumor progresses on therapy will be off-study. However, mild progression ( $\leq 25\%$  increase in tumor size) at the beginning of the treatment is allowed, given the usual delayed response / pseudoproggression seen with immunotherapy (Wolchok et al., 2009).

Patients who experience a SAE which triggers stopping rules for immune checkpoint inhibitors ipilimumab, nivolumab, or pembrolizumab as described in their respective package inserts will be permanently discontinued from the immune checkpoint inhibitor. They can be continued on dorgenmeltucel-L (if in Arm 1) once recovered from immune checkpoint inhibitor toxicity.

Patients are also off study who:

- experience intercurrent illness that prevents further administration of treatment;
- decide to withdraw from the study;
- experience general or specific changes in the patient's condition that render them unacceptable for further treatment in the judgment of the investigator.

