#### 4.5 *Off-Study Therapy Criteria*

Patients will be removed from study therapy when any of the criteria listed in Section 4.4 applies. The reason for study removal and the date the patient was removed must be documented on the Case Report Form.

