#### 4.6 *Post-Treatment Evaluation/Monitoring*

For patients who receive the immunotherapy and complete or go off-treatment early, follow up visits will be made until 5 years or death whichever comes first.

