**Follow Up Visits for ALL Subjects (after 1st FUV):**

- Imaging to be completed every 3 months until disease progression, after disease progression imaging is completed per standard of care
- Survival status checks to be completed at least every 3 months until death or lost to follow up
- All other assessments should be completed per standard of care practices.

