**For Patients with Measurable Disease (i.e., Target Disease)**

Target Lesions	Non-Target Lesions	New Lesions	Overall Response	Best Overall Response when Confirmation is Required*
CR	CR	No	CR	≥4 wks. Confirmation**
CR	Non-CR/Non-PD	No	PR	≥4 wks. Confirmation**
CR	Not evaluated	No	PR	
PR	Non-CR/Non-PD/not evaluated	No	PR	
SD	Non-CR/Non-PD/not evaluated	No	SD	documented at least once ≥4 wks. from baseline**
PD	Any	Yes or No	PD	no prior SD, PR or CR
Any	PD***	Yes or No	PD	
Any	Any	Yes	PD	

\* See RECIST 1.1 manuscript for further details on what is evidence of a new lesion.

\*\* Only for non-randomized trials with response as primary endpoint.  
 \*\*\* In exceptional circumstances, unequivocal progression in non-target lesions may be accepted as disease progression.

Note: Patients with a global deterioration of health status requiring discontinuation of treatment without objective evidence of disease progression at that time should be reported as “*symptomatic deterioration.*” Every effort should be made to document the objective progression even after discontinuation of treatment.

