## **12 STATISTICAL CONSIDERATIONS**

### ***12.1 Sample Size***

This study was originally designed to compare the response rates between the combined dorgenmeltucel-L plus immune checkpoint therapy arm to the immune checkpoint therapy arm alone. During this study, enrollment will include a total of 100 evaluable patients across 2 treatment arms (50:50).

Assuming a disease control rate of 22% (Wolchok *et al.*) in the immune checkpoint monotherapy arm and a combined arm response rate of 42%, a total of 100 patients (1:1 ratio) will be required to assess superiority of response rate with 80% power and two-sided alpha of 0.20.

As the primary endpoint has been changed from overall response rate to PFS, 50 patients per treatment arm (100 patients total) will provide 70% power to detect a hazard ratio of 0.6895 and 80% power to detect a hazard ratio of 0.6435, assuming the immune checkpoint monotherapy control arm has a median time to disease progression of 3 months and a two-sided type I error rate of 0.20. A total of 96 events are required for analysis.

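### Sections 4.4 and 4.5 do not separate stopping treatment from leaving the study, so a site could end tumour imaging before progression, against the all-subject imaging rule in Section 8

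*Combined protocol and SAP*

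**What the plan says.** **Text that can end follow-up at treatment stop**

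- Section 4.4 (Duration of Therapy) first takes patients off study for progression, then adds a list: "Patients are also off study who" have an intercurrent illness that prevents further dosing, withdraw, or have a change in condition that the investigator judges to rule out further treatment.
- Section 4.5 (Off-Study Therapy Criteria) reads that list as a treatment rule: "Patients will be removed from study therapy when any of the criteria listed in Section 4.4 applies". Its next sentence asks the case report form for the reason and date of study removal. Only one date is requested.
- The synopsis schemas for Arms 2A, 2B and 2C say that patients who progress go off study and are then followed for survival.
- Section 4.6 adds: "For patients who receive the immunotherapy and complete or go off-treatment early, follow up visits will be made until 5 years or death".

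**Text that keeps follow-up going**

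- Section 8, under the heading for follow-up visits of all subjects: "Imaging to be completed every 3 months until disease progression, after disease progression imaging is completed per standard of care". Survival checks continue at least every 3 months.
- Section 9.1, note on symptomatic deterioration: "Every effort should be made to document the objective progression even after discontinuation of treatment".
- Section 9.1 also sets tumour assessments about every 3 months in all treatment arms.

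**Analysis**

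PFS by RECIST v1.1 is the primary efficacy endpoint, analysed in all randomized subjects (Section 12.3) of an open-label trial (Section 12.2). Section 12.1 requires 96 events. Under Missing Data, Section 12.3 censors subjects without any efficacy evaluation at time 0 and leaves endpoint-specific imputation rules to the statistical analysis plan.

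**The concern.** An analysis of PFS in all randomized patients needs scans after treatment has stopped, up to progression or death. Two of the three entries in Section 4.4 are reasons to stop dosing, not reasons to stop observing. If a site gives off study the meaning it has in the Arm 2 schemas, it keeps the survival checks and drops the scans. A site working from Section 8 does the opposite with the same patient.

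A patient removed because of a worsening condition may well be near progression. Censoring that patient at the last scan, or at time 0 if no scan has been made, would then be informative, and the log-rank test assumes that it is not. The judgement is made by an investigator who knows the arm. Scans that were not made cannot be recovered by an analysis rule written later.

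**Working it through.** **1. The plan's own figure.** Inputs from Section 12.1: "50 patients per treatment arm (100 patients total) will provide 70% power to detect a hazard ratio of 0.6895", "80% power to detect a hazard ratio of 0.6435", "two-sided type I error rate of 0.20", control median 3 months, 96 events. Freedman's formula is d = (z₁ + z₂)² × [(1 + HR)/(1 − HR)]², with z₁ = 1.2816 for two-sided alpha 0.20.

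- HR 0.6435, 80% power (z₂ = 0.8416): 2.1232² × (1.6435/0.3565)² = 4.508 × 21.25 = 95.8, so 96 events.
- HR 0.6895, 70% power (z₂ = 0.5244): 1.8060² × (1.6895/0.3105)² = 3.262 × 29.61 = 96.6, so 97 events.
- At 96 events, Freedman power is 80.1% and 69.8%.

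The stated design reproduces.

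**2. The margin.** 100 − 96 = 4. A fifth patient without a PFS event puts 96 out of reach. With exponential PFS, 96% of patients have had an event only after about 17.4 months of follow-up each (HR 0.6895) or 18.3 months (HR 0.6435), so scanning has to last well beyond many treatment stops.

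**3. Loss of events alone.** If the censoring is unrelated to prognosis, power = Φ(½√d × |ln HR| − 1.2816). The documents give no loss rate, so these shares are assumed.

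| Share censored early | Events | Power, HR 0.6895 | Power, HR 0.6435 |
|---|---|---|---|
| none | 96 | 70.5% | 81.0% |
| 10% | 90 | 68.5% | 79.1% |
| 20% | 80 | 64.8% | 75.5% |
| 30% | 70 | 60.8% | 71.3% |

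**4. Informative loss.** This was simulated with 50 patients per arm, exponential PFS, a control median of 3 months, scans every 3 months, two-sided alpha 0.20, and each lost patient censored at the scan before progression. The loss shares, their placement by arm and the timing of censoring are all assumptions. Ranges are over repeated simulations.

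| Loss | Apparent HR when the true HR is 1 | Power at HR 0.6435 |
|---|---|---|
| none | 1.00 | 81% |
| 5%, control only | 1.05 to 1.06 | 74 to 75% |
| 10%, control only | 1.11 to 1.12 | 65 to 66% |
| 20%, control only | 1.25 to 1.26 | 47 to 49% |
| 10%, both arms | about 1.00 | about 80% |
| 20%, both arms | about 1.00 | about 76% |

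As a rough check, removing a fraction f of control events scales the control hazard by (1 − f), so the apparent HR is 1/(1 − f): 1/0.95 = 1.05, 1/0.90 = 1.11 and 1/0.80 = 1.25. If the loss fell in Arm 1 instead, the bias would favour the vaccine. The chance of a false positive in its favour would rise from about 10% to roughly 14%, 17% and 31%.

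**5. What decides the size.** Steps 3 and 4 agree when loss is equal: the cost is a few points of power. The large effects appear only when informative loss is concentrated in one arm.

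**The case against.** The strongest reply is that the protocol already settles the matter.

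- Section 4.4 is about duration of therapy, and Section 4.5 applies its list to therapy.
- Off study does not end all contact. Section 10.6 recommends yearly visits even for subjects off study, and Section 9.1 (New Lesion Measurement) asks for tumour assessments after RECIST progression.
- Section 8 has the all-subject imaging rule, and the calendars for Arms 2A, 2B and 2C each have a first follow-up visit with radiologic evaluation.
- The symptomatic-deterioration note in Section 9.1 addresses the very patients whose censoring would be informative.

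This stands as far as intent goes: a site that follows Sections 8 and 9 loses nothing. It does not remove the conflict. Section 4.5 still records a treatment stop as study removal, and the Arm 2 schemas still attach survival follow-up alone to off study.

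A reader might go further and infer that control patients are systematically dropped. Two points suggest it. Section 4.6 provides visits for recipients of the immunotherapy, which in Sections 4.1 and 4.2 is the vaccine. And after checkpoint-inhibitor toxicity only Arm 1 patients have a study treatment to continue. The documents do not support that inference:

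- Checkpoint-inhibitor toxicity has its own paragraph in Section 4.4 and is not on the off-study list.
- Section 4.6 does not mention imaging and is not worded as exclusive. It sits beside the gene-transfer monitoring, so it can be read as safety follow-up.
- Section 5 also calls the checkpoint inhibitors immunotherapies.

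**Conclusion.** The conflict is real and should be resolved. It is an ambiguity that could cut imaging short, not evidence that PFS will be truncated. The reproduced design figures of 96 events and about 70% and 80% power do not change.

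The size and direction of any bias cannot be derived from the documents. Under the assumptions above, the effect at 10% loss runs from almost none (equal loss, power about 80%) to a null hazard ratio of about 1.1 and power of about 65% (control-only loss). An imbalance between arms is possible but not established, so the one-arm figures illustrate what could happen and are not a forecast. What does follow directly from the plan is the narrow margin of 4 patients without an event.

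**What to change.** 1. In Sections 4.4 and 4.5, replace off study with off study treatment for every non-progression reason except withdrawal of consent to follow-up.
2. State there, with reference to the all-subject follow-up rule in Section 8, that imaging continues every 3 months until RECIST progression and survival checks until death, in both arms and whatever the reason for stopping.
3. On the case report form, record end of treatment and end of follow-up as separate dates with separate reasons.
4. In Section 4.6, add only a cross-reference saying that Section 8 governs tumour and survival follow-up for all randomized patients. Rewording the section to cover both arms could give control patients the 5-year visit schedule as well, which this point does not call for.

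The cost is an amendment to the wording and one more date and reason on the form. No treatment rule or design figure changes. The downside is that sites must pursue some patients who are off treatment for scans, but Section 8 already requires those scans.

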#### 4.5 *Off-Study Therapy Criteria*

Patients will be removed from study therapy when any of the criteria listed in Section 4.4 applies. The reason for study removal and the date the patient was removed must be documented on the Case Report Form.

#### 4.6 *Post-Treatment Evaluation/Monitoring*

For patients who receive the immunotherapy and complete or go off-treatment early, follow up visits will be made until 5 years or death whichever comes first.

#### **Long-term Clinical Monitoring of Subjects Participating in this Gene Transfer Trial.**

Subjects surviving for more than 2 years will be followed on a yearly basis for at least 13 additional years (15 years total) as recommended by the FDA Biologic Response Modifier's Advisory Committee (BRMAC) for late sequelae of gene transfer.

Information to be collected and made available to the FDA in the IND annual report and reports to other regulatory agencies as mandated will include:

- Clinical information on *de novo* cancers, neurological, autoimmune and hematological disorders.
- Unexpected medical problems, hospitalizations and medications.
- Expected or unexpected patient death and cause of death.

## 5 **DOSING INFORMATION**

The study is designed to evaluate the addition of dorgenmeltucel-L to standard of care checkpoint immunotherapy. The following information about ipilimumab, nivolumab, and pembrolizumab is provided as background and drawn from the package inserts of the respective immunotherapies. The information should not be considered complete nor comprehensive. The administration of

these agents (ipilimumab, nivolumab, and pembrolizumab) should be done at the direction of the treating physician according to the physician's usual standard of care practices.

### 5.1 Dorgenmeltucel-L Immunotherapy

Dorgenmeltucel-L immunotherapy consists of equal quantities of three cellular components. The cellular components (HAM-1, HAM-2, and HAM-3) of dorgenmeltucel-L immunotherapy have been derived from allogeneic melanoma cancer cell lines. HAM-1 is derived from the human melanoma cell line G361, HAM-2 is derived from the melanoma cell line SK-MEL28, and HAM-3 is derived from the human melanoma cell line COLO829. Master cell banks of these cellular components have been engineered to express the murine  $\alpha(1,3)$ GT gene. During manufacturing the cells are amplified and harvested under sterile culture conditions then irradiated. The product is then stored in the vapor phase of liquid nitrogen until released for shipment. All production lots are subjected to testing to assure compliance with all product specifications before they are released for clinical use.

The immunotherapy cells (HAM-1, HAM-2, HAM-3) are supplied individually packaged in sterile 1.0 mL gasket-sealed cryovials. Each vial contains a cell suspension in a neutral saline solution with human albumin (USP) and glycerine (USP). After thawing, the content of the vials is a turbid yellow-white liquid. Injections must be administered within 30 minutes of thawing the immunotherapy.

For administration, each of the three immunotherapy cellular components is administered separately. Patients receive a total of six (6) injections per immunization procedure. The component specifications are listed in **Table 3** below.

**Table 3. Immunotherapy Specifications**

Dorgenmeltucel-L	Fill Volume	# Cells per Vial	Vial Size	Volume to be Injected	Volume per each Injection	Total Cells per Treatment	# of Injections
HAM1	0.65 mL	$6.5 \times 10^7$	2 x 1.0 mL	1.0 mL	0.5 mL	100 M	2
HAM2	0.65 mL	$6.5 \times 10^7$	2 x 1.0 mL	1.0 mL	0.5 mL	100 M	2
HAM3	0.65 mL	$6.5 \times 10^7$	2 x 1.0 mL	1.0 mL	0.5 mL	100 M	2
TOTAL			6 vials	3 mL		300 M	6

The dose of dorgenmeltucel-L immunotherapy given in this study is 300 million HAM cells. When giving a dose of 300M HAM cells, the clinical site will give 6 injections (2 injections of 0.5 mL of HAM1 + 2 injections of 0.5 mL of HAM2 + 2 injections of 0.5 mL of HAM3).

The HAM immunotherapy cells are injected intradermally (i.d.) using a small (tuberculin) syringe with a #25-gauge needle. Injections are split between the forearms and thighs on a rotating basis at each immunization.

For preparation for injection see **Appendix C**.

**Specific Risk/Adverse Events to HyperAcute immunotherapy**

A number of patients receiving HyperAcute immunotherapy (for cancers of the lung, pancreas, and skin) experience skin reactions at the site of immunization. The types of inflammatory response observed varied among individuals. The following skin reactions have been observed:

**A) Acute Reaction**

In most cases, patients receiving HyperAcute immunotherapy experience a rapid inflammatory reaction at the site of injection. This reaction is characterized by swelling, erythema, heat in the area, mild discomfort and itching.

**B) Delayed Type Hypersensitivity reactions**

Some patients also experience a DTH-like reaction. In this case the inflammatory response takes two to three days to develop.

The following reactions have been observed during, immediately after an immunization, and/or 2-5 days later:

- Pain
- Erythema (Redness)
- Pruritus (Itching)
- Swelling
- Induration (Hardening)
- Irritation/Discomfort
- Warmness

To help alleviate any discomfort that the patient might experience, due to an adverse reaction at the injection site, the following treatment options are acceptable:

- First try ice or cold compresses to the area
- If itching/discomfort continues, diphenhydramine cream (or appropriate alternative anti-histamine cream) can be used
- If itching/discomfort is not alleviated with topical cream, oral diphenhydramine (or appropriate alternative anti-histamine) may be used
- Acetaminophen or ibuprofen can also be used for pain/discomfort

The most frequently reported HyperAcute-related adverse events (all grades) experienced in the Melanoma Clinical Trials 0104 and OCI-01 are injection site reactions, fatigue, and nausea.

For more details on adverse events observed, please see the Investigator's Brochure for dorgenmeltucel-L immunotherapy.

**Procurement**

The allogeneic dorgenmeltucel-L immunotherapy is prepared, vialled, supplied and shipped by NewLink Genetics Corporation. Dorgenmeltucel-L is shipped by air carrier to the clinical site on dry ice. Each shipment is accompanied by Clinical Investigational Material Shipment Receipt Form and a Certificate of Analysis for product safety testing. Upon receipt, at the clinical site, the product is unpacked by a designated person(s) and immediately transferred to the vapor phase of

a liquid nitrogen storage tank. The drug will be stored in the clinical site's Investigational Pharmacy or designated area in a monitored liquid nitrogen cryofreezer under strict QC conditions. The procedure for preparation is outlined in **Appendix C**.

### **Drug Accountability**

FDA regulations require investigators to establish a record of the receipt, use, and disposition of all investigational agents. Investigators may delegate responsibility for drug ordering, storage, accountability and preparation to his/her designee. The investigator, or the responsible party designated by the investigator, must maintain a careful record of the inventory and disposition of all agents received.

## **5.2 Ipilimumab (Yervoy®) – Information from package insert**

### **Description**

Ipilimumab (Yervoy) is a recombinant, human monoclonal antibody that binds to the cytotoxic T-lymphocyte-associated antigen 4 (CTLA-4). Ipilimumab is an IgG1 kappa immunoglobulin with an approximate molecular weight of 148 kDa. Ipilimumab is produced in mammalian (Chinese hamster ovary) cell culture.

### **Mechanism of Action**

CTLA-4 is a negative regulator of T-cell activation. Ipilimumab binds to CTLA-4 and blocks the interaction of CTLA-4 with its ligands, CD80/CD86. Blockade of CTLA-4 has been shown to augment T-cell activation and proliferation. The mechanism of action of ipilimumab's effect in patients with melanoma is indirect, possibly through T-cell mediated anti-tumor immune responses.

### **Pharmacokinetics**

The pharmacokinetics of ipilimumab was studied in 499 patients with unresectable or metastatic melanoma who received doses of 0.3, 3, or 10 mg/kg administered once every 3 weeks for four doses. Peak concentration ( $C_{max}$ ), trough concentration ( $C_{min}$ ), and area under the curve (AUC) of ipilimumab were found to be dose proportional within the dose range examined. Upon repeated dosing of YERVOY administered every 3 weeks, ipilimumab clearance was found to be time-invariant, and minimal systemic accumulation was observed as evident by an accumulation index of 1.5-fold or less. Ipilimumab steady-state concentration was reached by the third dose. The following mean (percent coefficient of variation) parameters were generated through population pharmacokinetic analysis: terminal half-life of 14.7 days (30.1%); systemic clearance (CL) of 15.3 mL/h (38.5%); and volume of distribution at steady-state ( $V_{ss}$ ) of 7.21 L (10.5%). The mean ( $\pm$ SD) ipilimumab  $C_{min}$  achieved at steady-state with the 3-mg/kg regimen was 21.8 mcg/mL ( $\pm$ 11.2).

*Specific Populations:* Cross-study analyses were performed on data from patients with a variety of conditions, including 420 patients with melanoma who received single or multiple infusions of ipilimumab at doses of 0.3, 3, or 10 mg/kg. The effects of various covariates on ipilimumab pharmacokinetics were assessed in population pharmacokinetic analyses.

Ipilimumab CL increased with increasing body weight; however, no dose adjustment of ipilimumab is required for body weight after administration on a mg/kg basis. The following

factors had no clinically meaningful effect on the CL of ipilimumab: age (range 26 to 86 years), gender, concomitant use of budesonide, performance status, HLA-A2\*0201 status, positive anti-ipilimumab antibody status, prior use of systemic anticancer therapy, or baseline lactate dehydrogenase (LDH) levels. The effect of race was not examined as there were insufficient numbers of patients in non-Caucasian ethnic groups.

*Renal Impairment:* Creatinine clearance at baseline did not have a clinically important effect on ipilimumab pharmacokinetics in patients with calculated creatinine clearance values of 29 mL/min or greater.

*Hepatic Impairment:* Baseline AST, total bilirubin, and ALT levels did not have a clinically important effect on ipilimumab pharmacokinetics in patients with various degrees of hepatic impairment.

